[^] C= Child, G=Guardian, LC=Lay Counselor; RC: Research Coder (i.e., Data entry person) [*] BL = Baseline; 12w = 12-14 weeks; 6M = 6 months; 12M = 12 months [#] Post-T = Post-Training; Post C1: after delivery of one 1 cycle of groups (2 groups); Post C2: after delivery of 2 nd cycle of groups [†] Measure used in the TF-CBT for CTG Feasibility Study ⁺ Measures used in POFO (both TZ and KE)			

3C5. Data Analysis Plan

Basic data screening procedures will be conducted (e.g., means, standard deviations, skewness, plotting relationships) to screen for errors and explore normality, linearity, form, and outliers. Data will be transformed as appropriate. We will confirm the assumption of randomization at baseline by testing cohort differences in outcome variables (i.e. symptoms), history of traumatic events and basic demographics (i.e. gender and age). Minor differences will be controlled for in statistical models as described below. Statistical analyses for the main aims will be conducted using the SPSS¹¹⁸, Stata¹¹⁹ and Multilevel/Hierarchical Level Modeling¹²⁰ (MLM/HLM) software programs. HLM allows for the presence of missing data at Level 1 (such as when participants are lost to follow-up) appropriately adjusting for data missing at random, particularly when covariates associated with missingness are included in the statistical model¹²¹.

3C5a. Overview of Modeling Approach. Hypotheses related to Aim 1 will be tested using MLM (i.e. HLM, random coefficient models, mixed effects models), which are a powerful and flexible class of analytic approaches that allow for the analysis of non-independent data. MLM allow researchers to account for nesting within different data structures and to explicitly model effects across nested groups. For the current study, the outcome data will be observations of clinical outcomes at multiple time points, nested within children, who are also nested within TF-CBT groups (for the TF-CBT condition). Not accounting for the fact that some children are treated in the same treatment group, for example, could lead to biased estimates. The MLM approach reduces Type I errors caused by violating assumptions of independence, allows time-varying assessments and increases power by utilizing information from multiple time points in a single model.

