We will test hypotheses through a standard approach to model-building, focusing on creating parsimonious explanatory models through progressive taxonomies as follows^{122,123}. An unconditional model (i.e. one without predictors) of the outcome will be fitted first, which allows specification of the random effects, which in turn provides an estimation of the amount of interdependence at each level of clustering. For longitudinal models including multiple time points (i.e. client outcomes from baseline to follow up assessments), an unconditional growth model will be fit to identify time trends and inter-individual variance in trends. We will next test the effects of the primary variable of interest (e.g., condition assignment, or therapist fidelity to treatment model) on the outcome in a conditional model (i.e., one with predictors). Finally, theoretically relevant covariates will be

added to determine the robustness of the main effects. Relative goodness-of-fit for each successive model will be evaluated using likelihood ratio tests and deviance statistics.

3C5b. Primary Analyses

Aim 1. Test the effectiveness of a group model of TF-CBT for orphaned youth in two East African countries, including any variation by child age and gender.

Hypothesis 1: Children in the TF-CBT condition will demonstrate greater reductions in symptoms and greater improvement in overall functioning and the child-guardian relationship.

These analyses focus on whether TF-CBT produces significant reductions in symptoms (i.e. CTG, PTS, depression, behavioral problems) or improvement in functioning, or the child-guardian relationship compared to UC. Hypotheses will be tested in two ways using MLM. First, we test whether the TF-CBT condition differs from the UC condition at 12-weeks (i.e., end of TF-CBT). This hypothesis will be tested with a simple 2-level MLM, predicting the observed outcome (by child or guardian report) at 12-weeks, while accounting for clustering of individuals within TF-CBT groups, for the TF-CBT condition. The general Level 1 equation, which models individual differences in symptoms at 12-weeks, would be as follows:

Level 1:	$Symptoms_{ig} = B_{0g} + B_{1g}PreSx + B_{2g}Cov + e_{ig}$
Level 2:	$B_{0g} = \pi_{00} + \pi_{01}Treatment + r_{00}$ $B_{1g} = \pi_{10} + r_{00}$ $B_{2g} = \pi_{20}$

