For example, where the outcome is the level of symptoms for a given client i in group g ; B_{0g} (the intercept) represents the average 12-weeks level of symptoms for all children in a given group g , B_{1g} is the effect of pre-treatment symptoms, B_{2g} is the effect of

child/guardian-level covariates (such as demographics: child age, gender), and e_{it} represents residual variance in the outcome for individual i in group g . If randomization was effective, the effects of pre-treatment symptoms may be ignored. The Level 2 equations represent how the coefficients at Level 1 are distributed across treatment groups. Both the intercept and the effects of pre-treatment symptoms (if needed) would be specified as random variables, which would allow their effects to differ across treatment groups. The level 2 equation would follow the general form of $B_{0g} = \pi_{00} + \pi_{01}Treatment + r_{00}$, which uses condition-level variables (such as assignment to TF-CBT or UC) to predict how effects differ. Thus the hypothesis that group-based TF-CBT produces significant improvements in symptoms over the UC condition would be tested by evaluating the significance of π_{01} above, which tests the effects of condition assignment on 12-week symptoms.

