3C5c Power. Power analyses were conducted using Optimal Design 2.0¹²⁴. A primary concern when estimating power in HLM focuses on the Interclass Correlation Coefficient (ICC) for providers, as providers are nested within conditions. Higher positive ICCs result in less statistical power, and few estimates of provider ICCs for fidelity to treatment are available. A review of 20 studies predicting client functioning found provider ICCs clustering from -0.1 to .06¹²⁵. Because precise estimates for ICCs are unknown, we examined ICC thresholds within a range of effect sizes (with .05 Type I error rate, power of .80, 8 children per TF-CBT group; 320 children total). Estimates did not include the effect of covariates which, if moderately correlated with the outcome variable, will increase statistical power. Therefore, these estimates present a conservative estimate. Our primary hypothesis test (i.e. differences at 12-weeks between TF-CBT & UC) is sufficiently powered ($1-\beta = .80$) to detect small effects (.35) with ICCs up to .15, moderate effects (.50) with ICCs up to .30, and all conceivable large effects. For detecting condition differences in terms of the linear or quadratic slope, analyses suggested that the proposed *N* has power ($1-\beta = .80$) to detect effects as small as .29 on slopes. Finally, for Aim 3, the current sample of 320 individuals in the TF-CBT condition, the current study is sufficiently powered to detect small (.21) effects of individual implementation variables on outcomes, but with only 20 clusters (i.e., groups) the study will have less power to detect all but large effects of group-level variables (e.g., fidelity).

3C6. Rationale of Choices Made in the Research Design. Our team carefully considered various design and methodological challenges, our rationale for various decisions is discussed here.

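### The primary 12-week test is a complete-case analysis: its protection against missing data rests wholly on covariates, and the plan allows the most important one, the baseline score, to be dropped

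*Combined protocol and SAP*

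**What the plan says.** Section 3C5 (Data Analysis Plan) makes one general statement about missing outcomes: "HLM allows for the presence of missing data at Level 1 (such as when participants are lost to follow-up", described as "appropriately adjusting for data missing at random, particularly when covariates associated with missingness are included in the statistical model". Section 3C5a then describes outcomes measured at several times within each child.

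Section 3C5b, Aim 1, specifies a different structure for the 12-week comparison: "This hypothesis will be tested with a simple 2-level MLM, predicting the observed outcome (by child or guardian report) at 12-weeks". In its equations child *i* is at Level 1 and group *g* at Level 2. Section 3C5c identifies this as the main test: "Our primary hypothesis test (i.e. differences at 12-weeks between TF-CBT & UC) is sufficiently powered".

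The baseline score (PreSx) appears in the Level 1 equation, but 3C5b adds: "If randomization was effective, the effects of pre-treatment symptoms may be ignored". The other covariates are given only by example, as "child/guardian-level covariates (such as demographics: child age, gender" and so on. No predictors of missing visits are named.

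The three-level growth model in 3C5b uses every visit. It is worded as a possible expansion, and its intercept may be placed at 12 months. The plan gives no expected dropout rate, no imputation and no sensitivity analysis for missing outcomes.

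**The concern.** Tolerance of missing Level 1 data helps when Level 1 is the visit, because a child who misses one visit still contributes the others. In the primary test each child has one outcome row. A child without a 12-14 week score has no row, and the 6- and 12-month scores of a dyad that returns do not enter.

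What protection remains comes from the covariates. Section 3C5b ties the need for the baseline score to whether randomization worked. Balance at baseline, however, describes everyone randomized; it says nothing about who later misses the 12-14 week visit.

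Loss that differs by arm is plausible, though not shown. TF-CBT dyads have 12 group and 3 individual sessions over 12 weeks (3C3a), while usual-care dyads have no scheduled study assessment between baseline and 12-14 weeks (3C4a). At stake is the size of the main treatment contrast.

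**Working it through.** **Plan's own figure.** The documents give no attrition rate, return rate or between-visit correlation, so there is nothing to reproduce on this point. The power statement in 3C5c is used only for an example effect, 0.35 SD.

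**Assumptions.** Scores are normal with SD 1. The correlation of baseline with each follow-up is 0.5, and between follow-ups 0.6. The true reduction is 0.35 at every follow-up. Loss at 12 weeks depends on a score *D*: a proportion *h* is lost above the arm's median of *D*, and *l* below it. Clustering is left out because it does not shift the expected estimates here.

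**Formulas.** The upper half of a standard normal has mean √(2/π) = 0.798. Among children still observed, the mean of *D* shifts by

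δ = 0.798 × (l − h) / (2 − h − l).

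Write r₁₂ and r₀ for the correlations of *D* with the 12-week and baseline scores, and Δ = δ(UC) − δ(TF-CBT). Then

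- estimate without baseline = 0.35 + r₁₂Δ
- estimate with baseline ≈ 0.35 + (r₁₂ − 0.5r₀)Δ

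**Values of δ.**

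- UC, 25% high and 5% low lost: 0.798 × (−0.20)/1.70 = −0.0939
- TF-CBT, 10% lost in both halves: 0
- TF-CBT, 5% high and 15% low lost: 0.798 × 0.10/1.80 = +0.0443

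**Results.**

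| Case | D | Δ | Without baseline | With baseline |
|---|---|---|---|---|
| A: UC 25%/5%, TF-CBT 10% | 6-month score | −0.0939 | 0.35 − 0.6×0.0939 = 0.294 | 0.35 − 0.35×0.0939 = 0.317 |
| B: UC 25%/5%, TF-CBT 5%/15% | 6-month score | −0.1382 | 0.35 − 0.6×0.1382 = 0.267 | 0.35 − 0.35×0.1382 = 0.302 |
| C: as A | baseline | −0.0939 | 0.35 − 0.5×0.0939 = 0.303 | 0.35 + 0 = 0.350 |
| D: as A, UC pattern reversed | 6-month score | +0.0939 | 0.406 | 0.383 |
| E: 25%/5% in both arms | 6-month score | 0 | 0.350 | 0.350 |
| F: as A | unseen 12-week score | −0.0939 | 0.35 − 0.0939 = 0.256 | 0.35 − 0.75×0.0939 = 0.280 |

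Simulation with 1,000,000 children per arm agrees with these values to within about 0.003.

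**Using all visits.** In the same simulation, missing 12-week scores were predicted within arm from all observed visits, a likelihood-type estimate.

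- Cases A and B, all missed dyads returning: 0.35.
- Case A with partial return: about 0.335 at 50%, 0.327 at 25%, and 0.317 at 0%. The last equals the 12-week model with baseline.
- Case F, all returning: about 0.30, against 0.28 from the 12-week model with baseline.

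**Scale.** With 320 per arm, 8 per TF-CBT group, ICC 0.15 and no covariates, the standard error is √[(1 + 7×0.15)/320 + 1/320] = √(3.05/320) = 0.098. With baseline, the shortfalls in A and B are 0.033 and 0.048, or 0.34 and 0.49 of a standard error. Without baseline they are 0.056 and 0.083, or 0.58 and 0.85.

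**The case against.** A reader might infer that the 12-week test has no protection at all against missing data. The documents do not support that. Section 3C5 claims adjustment only under missing at random and points to covariates related to missingness, and the 12-week equation contains both PreSx and covariates. If loss depends only on arm and variables kept in the model, the complete-case estimate is valid, as case C with baseline shows. For a child seen only at baseline, a longitudinal model adds essentially nothing more.

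Nor does it follow that dropping these children biases the contrast. Case E shows no bias and case D an upward one. The shortfalls in A and B need loss that differs by arm and follows later symptoms; the recovery by the all-visit model also needs dyads to return. None of this can be checked from the documents.

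It can also be said that the plan already includes a model of all visits, as the second of its two ways of testing the hypothesis. That is fair, and the plan does not lack a longitudinal analysis. But that model addresses the 12-month level and the rate of change, and does not supply the 12-week contrast.

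What stands is that the primary test is complete-case, that its validity rests on covariates, and that the plan permits the strongest of these to be left out.

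**Conclusion.** The point holds in conditional form. The general assurance in 3C5 overstates the protection for the primary 12-week test. The existence and direction of bias are not established. Under the assumed loss patterns in A and B, a true 0.35 SD becomes 0.30 to 0.32 with baseline and 0.27 to 0.29 without it. Where loss depends only on baseline, keeping the baseline score removes the whole error (0.35 against 0.30).

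The gain from later visits shrinks as fewer dyads return and vanishes if none do. It is only partial if loss depends on the unseen 12-week score. All loss rates, return rates and correlations are assumptions. The structural finding, one outcome row per child, follows from the plan's own equations and depends on none of them. The change is worth making because it uses data already to be collected.

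**What to change.** 1. Estimate the 12-week TF-CBT versus usual-care contrast from one repeated-measures mixed model of baseline, 12-14 weeks, 6 months and 12 months, with visit as a categorical factor, condition-by-visit terms and the TF-CBT group effect. Include every randomized dyad with any outcome, by assigned condition.
2. Always include the baseline score, and state in advance whether it enters as the first visit or as a covariate. Delete the 3C5b option to ignore it.
3. Keep the single-time-point model, with baseline, as a complete-case sensitivity analysis.
4. Limit the missing-data statement in 3C5 to the repeated-measures models.

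This changes analysis-plan wording only: no new data, visits or software. The cost is a somewhat more complex primary model. It does not resolve loss that depends on the unseen 12-week score, and the plan should say so.

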We propose a RCT of TF-CBT that builds on our feasibility study, with the goal of testing the effectiveness of an intervention that is locally feasible, acceptable, and holds promise for improving mental health outcomes and functioning of orphaned children. Although 8 RCTs of TF-CBT have been conducted in the US, there has never been a RCT of its effectiveness in LAMICs with high prevalence of HIV. The proposed trial, to be conducted in both Moshi, TZ and Bungoma, KE ($N = 640$, with 20 TF-CBT groups provided in each region), includes: (1) a usual care control group in each region, (2) independent research interviewers; and (3) enhanced ecological validity and local responsibility by including the lay counselors from the feasibility study to assist [name] and [name] in training and supervising the lay counselors.

3C2a. Outcomes Examined. We plan to examine clinical outcomes, which include CTG, PTS, PTSD, depressive symptoms, behavioral problems, as well as any effect on the child-guardian relationship and the child's overall daily functioning (the last of these is a tool to be developed locally in the first quarter of the study; see Tables 3 & 4). We also plan to describe and examine the impact of implementation factors (e.g., TF-CBT fidelity, lay counselor knowledge gain, guardian and child attendance) on clinical outcomes. With the increasing attention given to task-shifting approaches³² and their promise for reducing the mental health treatment gap, implementation efforts that incorporate feasible methods for building greater local responsibility and sustainability are needed.

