The proposed study is a rigorous test of clinical outcomes building on a training and supervision approach employed by [name] (consultant on this study)^{33,34}, [name]^{35,76}, and others³⁵ in RCTs in other LAMICs. This approach involves local, trained lay individuals (i.e., our feasibility study lay counselors) who act as the direct treatment model supervisors, under supervision themselves, by TF-CBT and mental health experts (i.e., [name] & [name]). Our team views this RCT as the first step in a broader research plan to test the effectiveness of TF-CBT in successive implementation stages that systematically increase local expertise and responsibility and decrease expert involvement, with the goal of enhancing our knowledge around effective, feasible, and sustainable implementation strategies in LAMICs. As stated in the recently released NIH/PEPFAR RFA, focused on HIV/AIDS specifically (i.e., RFA-AI-11-003): "scientific advances regarding the implementation of effective interventions have not kept pace."

3C2b. The comparison group for the RCT is a "usual care" (UC) condition (i.e., existing orphan support services; (see Section 3C3c for our preliminary studies on UC in TZ & KE; also see Human Subjects). We enroll 320 child-guardian dyads in each of the two conditions (TF-CBT & UC; 640 total), with half of the participants enrolled in TZ and half in KE (see Table 2). Both sites are mixed urban and rural areas, allowing testing of TF-CBT in both settings to examine any impact of setting variables (i.e. differences in UC; urban vs. rural) on clinical outcomes or implementation (e.g., fidelity, attendance). Equal numbers of males and females, and children in age groups 7-10 and 11-13 will be recruited for both TF-CBT and UC. In the POFO study we easily recruited nearly twice this number (e.g., 560) in each region, indicating that the population of OAC in the areas in which we plan to recruit are high enough to support the proposed sample.

Sample size estimates for the RCT were determined using effect sizes from TF-CBT RCTs conducted in the US^{81,104}, from outcomes obtained in our TZ feasibility trial, and data from the Zambia TF-CBT feasibility trial (see Section 3C5b; for Power Analyses). Each site has a local UC group to enhance internal validity, given unique cultural, historical, political, religious, and ethnic differences, including relatively recent election riots experienced in KE.

	Moshi, TZ		Bungoma, KE	
	Urban	Rural	Urban	Rural

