3C3b. Training and Supervision of Lay Counselors. The proposed trial uses an apprenticeship model³³⁻³⁵ of implementation in which "local trainers" (i.e., the experienced lay counselors from the TZ feasibility study: [name], [name], & [name]) apprentice to the TF-CBT and mental health experts in training and supervising lay counselors. Our team will train 9 counselors in TZ and 9 counselors in KE (18 total), who will deliver 20 TF-CBT groups (10 urban; 10 rural) to 160 children in each region. Lay counselors within each region will be randomly assigned to groups (3 counselors per group; 2 lead the child group, 1 leads the guardian group), so that counselor effects are balanced across groups and setting (urban, rural). In preparation for the training, [name] and [name] will work with the local trainers to establish a training plan that allows the local trainers to pair with the TF-CBT and mental health experts in providing didactic information, modeling TF-CBT skills, and overseeing lay counselor role plays during the training. As in the feasibility study, the training will be 10 days and will include substantial opportunities for lay counselors to practice skills while receiving coaching and feedback. The training will be provided in Moshi, TZ at the end of year 1 (see Table 3), with the KE-based lay counselors and [name] travelling to Moshi to attend the training.

Lay counselors are supervised directly by the local trainers, who receive supervision and direction themselves, from [name] and [name]. Following the in-person training, the TF-CBT and mental health experts will provide training in how to set up and structure practice in supervision (during year 1) and supervision of groups (during year 2, when the intervention begins) for the lay counselors in both TZ and in KE.

We will be following established procedures used in other CBT trials that employ an apprenticeship model of CBT implementation^{33,34}. Local trainers will then provide supervision to the 18 counselors (9 in TZ, 9 in KE), while receiving weekly

ACTIVITIES	YEAR 1	YEAR 2	YEAR 3	YEAR 4	YEAR 5
Hiring					
Refine Coding Measure					
Functioning Measure Dev.					
Translation & IRB Sub					
Interviewer Training					
Local Trainer Preparation					
Lay Counselor Assessment					
Lay Counselor Training					
Lay Counselor Supervision					
Local Trainer Supervision					
Youth Enroll. & TF-CBT Groups					
Interviewer Supervision					
Youth & Guardian Assess.					

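### Eighteen counselors are shared across 40 TF-CBT groups but the models cluster by group only; if counselors differ, type I error is about .07 to .10 at counselor ICCs within the cited range

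*Combined protocol and SAP*

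**What the plan says.** Section 3C2 plans TF-CBT "with 20 TF-CBT groups provided in each region", hence 40 groups, and 3C2b states "We enroll 320 child-guardian dyads in each of the two conditions". Section 3C3b describes the staff: "Our team will train 9 counselors in TZ and 9 counselors in KE (18 total), who will deliver 20 TF-CBT groups" in each region, with "3 counselors per group; 2 lead the child group, 1 leads the guardian group". Counselors are randomly assigned to groups within region "so that counselor effects are balanced across groups and setting (urban, rural").

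Section 3C5a defines the nesting: repeated observations are "nested within children, who are also nested within TF-CBT groups (for the TF-CBT condition"). In 3C5b the 12-week Aim 1 model has two levels, child and group. The growth model adds time. Aim 2 adds country and setting as level 2 predictors. No model contains a counselor term.

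The power section (3C5c) opens from a different unit: "A primary concern when estimating power in HLM focuses on the Interclass Correlation Coefficient (ICC) for providers, as providers are nested within conditions". It cites a review with provider ICCs from -0.1 to .06 (as printed), then computes power with the group of eight as the cluster.

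**The concern.** A group random effect treats the 40 groups as independent draws. They are not, because any two groups in a country may share one or more of the same nine people. Variance between counselors therefore averages out over 18 individuals, while the model divides it by 40 groups.

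Random assignment of counselors does not remove this. It spreads counselors evenly over TF-CBT groups and over urban and rural settings, which helps comparisons inside the TF-CBT arm. UC has no TF-CBT counselors, so the average quality of the 18 who were hired stays whole in the TF-CBT v UC contrast.

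At stake is the confidence interval for the main comparison. Sections 3B and 3C8 look toward wider use of TF-CBT by later generations of lay counselors, and an interval that ignores counselor variation is too narrow for that use.

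**Working it through.** **Inputs from the documents.** 320 children per arm; 40 groups of 8; 18 counselors (9 per country); 3 counselors per group; alpha .05 (sidedness not stated, two-sided assumed); cited provider ICC range -0.1 to .06. Slots per counselor: 20 x 3 / 9 = 6.7 groups.

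**Assumptions.** Total SD 1. UC unclustered. Group ICC g = .03 apart from counselors. The documents give no split between counselor and group variance, so a range is shown. An individual counselor ICC c, averaged equally over three counselors, gives a team share t = c/3.

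**The plan's own power figure.** Section 3C5c claims power .80 for an effect of .35 with ICC up to .15. For 40 groups of 8 v 320 unclustered children, the variance is .15/40 + .85/320 + 1/320 = .00953, SE .098, and power is about .94. A conventional two-arm cluster layout gives .57 with 40 clusters and .86 with 80. None of these layouts returns .80. For the actual layout with group-only clustering, the stated figure is conservative. (3C5c also refers to 20 clusters among the 320 TF-CBT children, where 3C2 and 3C3b give 40.) The point below does not depend on this.

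**Formulas.**
- Variance under the group-only model: (t + g)/40 + (1 - t - g)/320 + 1/320.
- Variance with shared counselors: c/18 + g/40 + (1 - t - g)/320 + 1/320, where c/18 = t/6.
- Type I error: 2 x [1 - Phi(1.96 x SE_model / SE_true)].
- Detectable effect at power .80: 2.80 x SE_true (normal approximation).

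**Worked case, c = .06, t = .02.**
- Model: .00125 + .00297 + .00313 = .00734, SE .086.
- With counselors: .00333 + .00075 + .00297 + .00313 = .01018, SE .101.
- 1.96 x .0857/.1009 = 1.665, so type I error is .096. Detectable effect .28.

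| Individual ICC c | Team share t | Model SE | SE with counselors | Type I, formula | Type I, simulated | Simulated, multiple membership | Detectable effect |
|---|---|---|---|---|---|---|---|
| 0 | 0 | .083 | .083 | .050 | - | - | .23 |
| .03 | .01 | .084 | .092 | .073 | .070 | .051 | .26 |
| .06 | .02 | .086 | .101 | .096 | .103 | .060 | .28 |
| .12 | .04 | .088 | .116 | .136 | .150 | .078 | .32 |
| .18 | .06 | .091 | .129 | .169 | .158 | .064 | .36 |

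The simulated columns use 1,200 null trials per setting with the planned layout (Monte Carlo standard error about .006 at a true level of .05).

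**Sensitivity.**
- No counselor variance (group ICC .05; 6,000 trials per assignment scheme): the group-only test rejects at .043-.055, so the inflation comes from counselor sharing.
- All clustering due to counselors (g = 0): type I error .076, .10 and .18 at t = .01, .02 and .06.
- Total ICC at the plan's .15 (t = .02, g = .13): SE .098 v .111, type I error .085, detectable effect .31.
- Only the two child leaders matter, c = .06 (t = .03, g = .03): model .03/40 + .03/40 + .94/320 + 1/320 = .00756; with counselors .06/18 + .03/40 + .94/320 + 1/320 = .01015; SE .087 v .101, type I error about .09.

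**The case against.** The best case for the plan has three parts.

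*The 18 counselors can be treated as fixed.* Aim 1 concerns orphaned youth in two countries and names no population of counselors. Section 3C2a calls the trial a first step before further implementation stages. For inference limited to these 18 people, this route causes no inflation. That is a legitimate choice, but the plan does not make it. Section 3C5c discusses providers through an ICC, which is a random-effect quantity, and 3B and 3C8 look to use by other counselors. If the sponsor wants the narrower target, the plan should say so.

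*The size is unknown.* The cited range includes zero and negative values, and the documents do not divide clustering between counselor and group. This stands, and any figure must carry its condition. A reader might infer that a type I error of .16-.17 lies within the plan's own range. That requires a team share of .06, which is about .18 per counselor, three times the top of the cited range. It falls inside the range only if provider means the three-person team, which the documents do not say.

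*Power is not damaged.* This also largely stands. A reader might infer that the stated detectable effect fails once counselors are modelled. At an individual ICC of .06 the detectable effect is about .28, and about .31 when total ICC is .15. Both are below .35. Only the team-level reading brings it to about .36.

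**Conclusion.** The omission is certain from the text: 18 counselors are shared across 40 groups, and no Aim 1 or Aim 2 model has a term for them. Its effect is conditional on two things: that counselors differ, and that they are treated as a random sample, as the provider-ICC framing and the dissemination aim imply.

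Under those conditions, with group ICC .03 and equal sharing among three counselors, nominal .05 becomes about .07 at individual counselor ICC .03 and about .10 at .06. The documents do not support presenting .16-.17 as the expected size, saying that the standard error is too small whatever the counselor variance, or calling the trial underpowered on this ground. The analysis should be changed, since the remedy touches neither recruitment nor conduct.

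**What to change.** 1. In the Aim 1 and Aim 2 models, add a counselor random effect with multiple membership in the TF-CBT arm, beside the group effect. Use small-sample degrees of freedom (Kenward-Roger or Satterthwaite) so that the reference distribution reflects 18 counselors.
2. Prespecify weights that reflect role (two child leaders, one guardian leader), with equal weights of 1/3 as an alternative. Equal weights alone would ignore the division of roles in 3C3b.
3. Report the group-only model as a sensitivity analysis.
4. In 3C5c, say whether provider means one counselor or the team. Add the detectable effect with the counselor component: about .28 at individual ICC .06, and about .36 only if the team ICC is .06, both at group ICC .03.
5. Keep the group-to-counselor assignments, with role, in the analysis file. The group report contents listed in Table 4 do not mention counselor identity, although random assignment implies that it is known.

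The cost is more analysis work and a somewhat wider interval if counselors differ. No extra staff or participants are needed. With only 18 counselors the variance will be estimated imprecisely. In the simulations the multiple-membership model rejected at .05-.08, so it removes most of the inflation but not always all of it.
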